9.2. Sample Size and Power

For this prospective analysis we will have an estimated sample size of 3,010 patients. The sample size is computed for the population with minimum representation in the total sample. 2019 rates of PRRT were 15% in this population. Using a conservative estimation of 10% PRRT administration, and erring on the side of caution, our sample size and power justification is based on approximately 300 subjects (excluding HRQoL questionnaire completion rates). By the law of the minimum, all other treatment subgroups with representation above 10% will yield greater sample size and consequently higher powers for the below-stated differences

9.2.1. Aim 1

The primary objective of Aim 1 is to evaluate changes in HRQoL over time for each treatment. Calculations are based on using the EORTC QLQ-C30 as the primary HRQoL measure. Conservatively

estimating PRRT to be administered in 10% of patients and further expecting a response rate of 60% in the study, we would expect the PRRT group may have approximately 180 patients with complete HRQoL data. Using a repeated measures design with 1 within-subject factor (time: baseline, 6 months, 12 months, and 18 months), the design achieves the following power (Table 5) to detect a time effect for the corresponding mean change. Calculations are based on assuming an autocorrelation of 0.5 between measurements, a standard deviation of 18, and using a Wilks' Lambda Approximate F Test with a 5% significance level. The power will be higher if PRRT administration amounts to more than 10% of the prospective population.

Table 5: Alternative power for changes in EORTC QLQ-C30 within PRRT treated subgroup

MEAN CHANGE IN HRQOL OUTCOMES AT BASELINE, 6, 12 AND 18 MONTHS (RANGE 0-100)*	DIFFERENCE IN MEAN HRQOL SCORE (OVER EACH TIME POINT)	POWER*
65, 62, 59, 56	3-3-3	100%
65, 63, 61, 59	2-2-2	98.3%
65, 63.5, 62, 60.5	1.5-1.5-1.5	84.3%

* THE POWER APPLIES EQUALLY TO POSITIVE OR NEGATIVE SCORING SCALES.

9.2.2. Aim 2

The primary objective of Aim 2 is to evaluate the effect of common treatment sequences on progression-free survival. A lack of historical data on the frequency and number of different variations of treatment sequences, and progression-free survival (PFS) differences by treatment and line of treatment coupled with the likelihood treatment sequences will further differ between the 14 sites taking part in this study make *any realistic and meaningful* sample size and power calculations impossible. Analyses for this aim will be exploratory, and will leverage the use of time-varying covariates in combination with the conditional Cox regression model proposed by Prentice, Williams, and Peterson (PWP) as a means of addressing the heterogeneity evidenced in the data. However, to put into perspective potential PFS differences that may be detected between two treatments using purely hypothetical situations, the below table summarizes power achieved for varying combinations of median PFS differences and number of patients per treatment arm. Calculations are based on the following assumptions: 1:1 treatment allocation, 48 months of uniform accrual and 12 months of follow-up, no loss to follow-up or switching treatments, unadjusted for confounders, and using the Lakatos approximation for a two-sided log-rank test with a 5% significance level.

Table 6: Power determination for changes in median PFS

Median PFS		N Per Treatment Arm	Power
Treatment 1	Treatment 2		
12 months	24 months	45	0.79
		50	0.83
24 months	36 months	175	0.80
		190	0.83

9.2.3. Aim 3

The primary objective of Aim 3 is to evaluate renal toxicity associated with the administration of PRRT as measured by creatinine clearance loss over time. We are expecting 2 mL/min/1.73m² annual decline in creatinine clearance based on averaged long-term follow-up with the most common PRRT isotope 177-Lu [34]. The repeated measures design with 180 subjects and 1 within-subject factor (time: baseline, 6 months, 12 months, and 18 months) achieves 100% power to detect creatinine clearance loss of 2 mL/min/1.73m² by 6 months, 4 mL/min/1.73m² by 12 months and 6 mL/min/1.73m² by 18 months, when the Wilks' Lambda approximate F test is used with a significance level of 0.05, and assuming an

autocorrelation of 0.5 from one time point to the next and a standard deviation of 5 mL/min/1.73m². Should the standard deviation become unreasonably high in the order of 15 mL/min/1.73m², our sample size is large enough to achieve 99% power under the same parameter settings. In order to test Bonferroni-corrected pairwise differences, the individual tests will achieve 99.6% power to detect a clearance loss of 2 mL/min/1.73m² between two time points. The Bonferroni-corrected tests will be set at a significance level of 0.05/6.

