7.1. Primary Outcomes

- 1) **European Organization for Research and Treatment of Cancer - Quality of Life Questionnaire (EORTC QLQ-C30).** The EORTC QLQ-C30 is one of the most widely used HRQoL questionnaires in cancer research. A validated tool, it consists of 30 questions with a 4-point Likert scale (from “not at all” to “very much”) incorporating five functional scales (physical, role, cognitive, emotional, and social), three symptom scales (fatigue, pain, and nausea and vomiting), a global health status / QoL scale, and a number of single items assessing additional symptoms commonly reported by cancer patients (dyspnea, loss of appetite, insomnia, constipation and diarrhea) and perceived financial impact of the disease. Responses to the QLQ-C30 will be linearly transformed to a 0-100 scale using EORTC guidelines, a higher score represents a higher (“better”) level of functioning, or a higher (“worse”) level of symptoms. A mean difference of 10 points (positive or negative) has been widely accepted as the minimal clinically important difference (MCID) for the EORTC QLQ-C30 [58]. A specific MCID for carcinoid syndrome and NET has not been identified. However a recent study in advanced colorectal cancer has indicated MCIDs for improvement (deterioration) ranged from 6 to 18 (-11 to -5) points for within-group change and 5 to 15 (-10 to -4) for between-group change for the EORTC QLQ-C30, with summarized MICDs (in absolute values) per scale mostly ranging from 5 to 10 points [59]. An MCID was not identified in the literature for the QLQ-GI.NET21 module.

[Time Frame: Change in mean score across baseline, 6, 12, and 18 month time points.]

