- 2) **European Organization for Research and Treatment of Cancer - Quality of Life Questionnaire - Neuroendocrine Carcinoid Module (EORTC QLQ-GI.NET21)** The EORTC QLQ-C30 can be used in conjunction with the EORTC QLQ-GI.NET21 specific questionnaire, which comprises a total of 21 items: four single-item assessments relating to muscle and/or bone pain (MBP), body image (BI), information (INF) and sexual functioning (SX), together with 17 items organized into five proposed scales: endocrine symptoms (ED; three items), GI symptoms (GI; five items), treatment-related symptoms (TR; three items), social functioning (SF21; three items) and disease-related worries (DRW; three items). Responses to the QLQ-GINET21 will be linearly transformed to a 0-100 scale using EORTC guidelines, with higher scores reflecting more severe symptoms.

[Time Frame: Change in mean score across baseline, 6, 12, and 18 month time points.]

- 3) **Sequencing of treatment regimens from electronic medical records.** This will involve identifying which treatments a patient used during their follow-up, and also in what order they received treatment. Dates and types of therapy initiated will be pulled from each patients EMR in reference to the patient’s index date (date of diagnosis). We will also be asking patients about their treatments (self-reported) in the baseline survey to ascertain potential missed therapies in the EMR. We will be comparing the frequency (N) and proportion (%) of use of a variety of therapies (i.e.: SSAs, bevacizumab, cytotoxic chemotherapy, everolimus, Interferon alpha, embolization, PRRT, small molecule TKIs) and the effects of their ordering/sequencing on outcomes of symptom burden and HRQoL.

[Time Frame: Up to 5 years, baseline to end of follow-up]

- 4) **Renal function.** Glomerular filtration rate (GFR) is the best overall index of kidney function. Normal GFR declines with age, and varies according to sex, race and body size. We will calculate creatinine clearance loss [54] by combining individual level CDM and enrollment questionnaire data on sex, race, height, weight and serum creatinine mg/dl laboratory values at regular intervals before and after PRRT cycles until the end of follow-up.

[Time Frame: Change in eGFR from baseline to end of follow-up.]

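### Section 7.1 and Table 4 make two whole questionnaires the primary, powered Aim 1 quality-of-life outcome, but section 9.2.1 powers a single unnamed QLQ-C30 score

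*Protocol*

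**What the plan says.** Protocol section 7.1 (Primary Outcomes) lists QLQ-C30 as item 1 and QLQ-GI.NET21 as item 2, each assessed as the change in mean score over the four surveys. QLQ-C30 is described as five functional scales, "three symptom scales (fatigue, pain, and nausea and vomiting), a global health status / QoL scale", five single symptom items and one item on financial impact. QLQ-GI.NET21 is described as four single items "together with 17 items organized into five proposed scales". No total or summary score is described for either, and no scale is singled out.

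Table 4 places both instruments in one primary Aim 1 row and marks that row as powered.

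Section 9.2.1 is narrower: "Calculations are based on using the EORTC QLQ-C30 as the primary HRQoL measure". Its calculation rests on "assuming an autocorrelation of 0.5 between measurements, a standard deviation of 18", "using a Wilks' Lambda Approximate F Test with a 5% significance level", and a group size from "further expecting a response rate of 60% in the study" applied to a 10% share of PRRT patients, so that "we would expect the PRRT group may have approximately 180 patients with complete HRQoL data". Table 5 then gives 100%, 98.3% and 84.3% power for declines of 3, 2 and 1.5 points per visit, and its footnote says that this holds whichever way a scale is scored. The stated objective is change over time within each treatment. The only multiplicity correction in section 9 is 0.05/6 for pairs of time points in Aim 3.

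**The concern.** The protocol gives two answers to what the primary quality-of-life outcome is: two instruments in section 7.1 and Table 4, one in section 9.2.1. Neither reduces to a single score. Within QLQ-C30 a high value is good for functioning and bad for symptoms, so a mean score for the instrument has no defined meaning. Table 5 describes one score at a 5% level, and a reader cannot tell which one.

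What is at stake is how a primary result will be read. With up to 24 candidate scores and none designated, a change in one of them within a regimen cannot be tied to the 5% level in section 9.2.1. The powered label for QLQ-GI.NET21 also has no calculation behind it. Section 9.3 says that the analysis plan will be refined once descriptive information from Aims 1 and 2 is available, which leaves room to choose the headline scale after results have been seen.

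**Working it through.** **Count of scores (section 7.1).** QLQ-C30: 5 functional + 3 symptom + 1 global + 6 single items = 15. QLQ-GI.NET21: 5 scales + 4 single items = 9. Together 24.

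**Inputs for Table 5 (section 9.2.1).** n = 180 (about 300 PRRT patients × 60%), SD 18, correlation 0.5, four time points, α = 0.05.

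**Reproducing Table 5.** The one-group Wilks' Lambda test on three contrasts has an F reference distribution with 3 and 177 degrees of freedom. With equal correlation ρ between all pairs of visits, the noncentrality is λ = n Σ(m − m̄)² / [SD²(1 − ρ)]. The denominator is 324 × 0.5 = 162.

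| Decline per visit | Σ(m − m̄)² | λ | Power at 5% | Table 5 |
|---|---|---|---|---|
| 3 | 45 | 180 × 45/162 = 50.0 | 100.0% | 100% |
| 2 | 20 | 180 × 20/162 = 22.2 | 98.4% | 98.3% |
| 1.5 | 11.25 | 180 × 11.25/162 = 12.5 | 84.8% | 84.3% |

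Table 5 is therefore the power of one score at an unadjusted 5% level, under equal correlation 0.5.

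**Error rate if every primary score were tested at 5% (an inference).** For independent scores the chance of at least one false positive in a regimen with no true change is 1 − 0.95^k. For correlated scores it was simulated with equicorrelated 3-degree-of-freedom statistics. The between-scale correlations are assumptions; the protocol gives none.

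| Scores | Independent | 0.3 | 0.5 | 0.7 |
|---|---|---|---|---|
| 24 | 1 − 0.95²⁴ = 71% | 60% | 47% | 33% |
| 15 (QLQ-C30 only) | 1 − 0.95¹⁵ = 54% | 46% | 38% | 27% |

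**Power if 5% were held by Bonferroni.** The λ values are the same, with α = 0.05/24 = 0.00208 or 0.05/15 = 0.00333.

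| Decline per visit | Unadjusted | 15 scores | 24 scores |
|---|---|---|---|
| 3 | 100.0% | 99.97% | 99.95% |
| 2 | 98.4% | 87.8% | 84.6% |
| 1.5 | 84.8% | 51.9% | 46.2% |

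Bonferroni is conservative for correlated scores, so these are lower bounds on what a sharper method could achieve.

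**The case against.** The strongest reply has five parts.

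- **Testing each scale at 5% is not stated.** The 5% appears only as the level of the power calculation; section 9.1.1 sets no test level and no success rule. This stands. A reader might infer that the plan runs 24 tests per regimen at 5%, but the error rates above are conditional on that.
- **Choosing a scale and a multiplicity rule belongs in the SAP, and Aim 1 is descriptive (section 2.1).** This stands in part. A rule across scales may sit in the SAP. But the protocol itself names the primary outcome in three places and does so inconsistently. Section 9.2.1 also powers a hypothesis test for Aim 1, whereas only Aim 2 is labelled exploratory in section 9.
- **Table 5 does not depend on how many scales are analysed.** This stands. A reader might infer that its power fails unless one scale is fixed. In fact, without adjustment it holds for each scale with SD 18, and power falls only if the level is corrected.
- **The effects that matter are safe.** This largely stands. The 3-3-3 row is a 9-point total change, the closest to the 10-point minimal important difference in section 7.1, and it survives correction. The row that drops to 46% is a 4.5-point total change. At the 15% PRRT rate reported for 2019, n would be about 3,010 × 0.15 × 0.60 ≈ 270, and Bonferroni power over 24 scores would be about 98% (2-2-2) and 75% (1.5).
- **The number of regimens is not fixed.** This stands. One could multiply eight listed therapies by 24 scores to reach 192 tests, but the protocol sets no such family.

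**Conclusion.** The point holds as an inconsistency in the primary outcome. Section 7.1 and Table 4 name two instruments with 24 scores, section 9.2.1 treats one instrument as primary and powers one unnamed score, and no calculation supports the powered label for QLQ-GI.NET21. That much rests on the text alone.

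The error rates rest on two assumptions: that all primary scores would be tested at an unadjusted 5%, and the between-scale correlation. Even on the narrowest case examined (15 scores, correlation 0.7) the rate is 27%, about five times nominal. The power losses rest on a Bonferroni correction that the protocol does not propose, and they touch only the two smaller effects in Table 5. The documents do not support saying that the 5% level or the stated power must fail: if one QLQ-C30 scale were designated and SD 18 suited it, both would stand within a given regimen, under Table 5's own assumptions. The correction is worth making but does not threaten the study.

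**What to change.** Reconcile section 7.1, Table 4 and section 9.2.1 by naming one QLQ-C30 scale as the primary Aim 1 quality-of-life outcome before outcome data are examined. Global health status/QoL is a natural candidate, though nothing in the protocol singles it out; the sponsor should confirm that SD 18 fits whichever scale is chosen, so that Table 5 applies to it. List the other 14 QLQ-C30 scores and all nine QLQ-GI.NET21 scores as secondary, either reported plainly as such or with Holm or false-discovery-rate control within each regimen. Remove the powered label for QLQ-GI.NET21 in Table 4.

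This changes protocol wording only; data collection and sample size are unaffected. The cost is that the other scales can no longer be called primary.

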D4	Programmatic evaluation materials due to PCORI.	Submit document that demonstrates study progress and feasibility based on metrics provided by PCORI to awardee. PCORI initiates Programmatic Evaluation. Metrics will include: the validity of cohort identification and its size and characteristic; feasibility of recruitment; generalizability of the sample; feasibility of data linkages (if relevant); validity and completeness of study outcomes; suggestions of needed enhancements or revisions to study protocol, as well as associated timeline. PCORI will provide recommendations about proceeding to next steps of the study within 45 days.	7/1/2022		
D5	Patient enrollment (50%)	50% of participants (N = 1505) screened, enrolled, and consented to the study.	10/1/2022		
D	Report Submission	Submit Interim Progress Report to PCORI via the PCORI Online system accessed through: https://pcori.force.com/engagement	1/1/2023		
E1	Patient enrollment (75%)	75% of participants (N =2258) screened, enrolled, and consented to the study.	6/1/2023		
E2	Submit IRB Continuing approval	Submit IRB approval of revised study protocol via the PCORI Online system.	7/1/2023		
E3	Presentation to PCORnet Steering Committee	Annual presentation to PCORnet Steering Committee on progress of study, lessons learned, and recommendations for improvement of PCORnet infrastructure	7/1/2023		
E	Report Submission	Submit Interim Progress Report to PCORI via the PCORI Online system accessed through: https://pcori.force.com/engagement	7/1/2023		
F1	Develop dissemination plan for rare disease tools and resources	Submit dissemination plan to PCORI via PCORI Online system	1/1/2024		
F	Report Submission	Submit Interim Progress Report to PCORI via the PCORI Online system accessed through: https://pcori.force.com/engagement	1/1/2024		
G1	Patient enrollment (100%)	100% of participants (N = 3010) screened, enrolled, and consented to the study.	2/1/2024		

Milestone - Deliverable ID	Milestone - Deliverable Name	Description	Due Date	Completion date	Projected Completion Date
G2	Submit IRB Continuing approval	Submit IRB approval of revised study protocol via the PCORI Online system.	6/30/2024		
G3	Completion of Data Collection for All Study Aims	Awardee must ensure that all data collection for all study aims as specified in the research plan is completed	6/30/2024		

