G4	Completion of Data Analysis for All Study Aims	Awardee must ensure that all analysis and evaluation for all study aims as specified in the Research Plan are completed.	6/30/2024		
G5	Share computable phenotype for target rare disease	Rare disease phenotype submitted to phenotype repository	6/30/2024		
G6	Complete documentation for external use	Final data sets, analytic files and codebooks are made publicly available	6/30/2024		
G7	Dissemination	Complete dissemination of tools and resources to rare disease and research community and other stakeholders.	6/30/2024		
G8	Presentation to PCORnet Steering Committee	Annual presentation to PCORnet Steering Committee on progress of study, lessons learned, and recommendations for improvement of PCORnet infrastructure	6/30/2024		
G9	Primary Completion Date	An estimated Primary Completion Date must be provided when registering the study in Clinicaltrials.gov. For studies that are not clinical trials or non-prospective observational studies registered on ClinicalTrials.gov, the Awardee and PCORI shall agree on a primary completion date as a milestone that precedes the agreed-upon date to submit a Draft Final Research Report.	6/30/2024		
G	Final Progress Report	Submit Final Progress Report to PCORI via PCORI Online system accessed through: https://pcori.force.com/engagement	6/30/2024		
H	Draft Final Research Report Submission	Submit Draft Final Research Report per these instructions.	10/31/2024		
I	Results submitted to ClinicalTrials.gov or other applicable database	Awardee ensures results are submitted to ClinicalTrials.gov or other appropriate database. Results must be submitted to ClinicalTrials.gov no later than one month before submission of the Draft Final Research Report.	1/1/2025		
J	Draft Final Research Report Revisions	Upon receipt of written summary, and as applicable, PI will make revisions and submit revised Draft Final Research Report and disposition of comments table for acceptance in accordance to PCORI policy and process.	4/30/2025		
K	Approval/sign off of the Lay Abstract	No later than 90 days beyond the date PCORI accepts the final report			
L	Contract Term Date				
M	Notification of Publication Acceptance	See Contract for instructions			
*Completion Indicator Key: Deliverables highlighted in light green indicate completed tasks, those in light orange are currently in progress, those in light red are delayed, and those not color coded await future completion.					

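### Section 9.2.1 counts about 180 PRRT patients with all four surveys, but Table 8 closes data collection on 6/30/2024, by when about 107 could have finished if its accrual dates are met; the dates and the n must be reconciled

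*Protocol*

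**What the plan says.** Protocol section 9.2.1 (Aim 1) starts from 3,010 patients, assumes that 10% receive PRRT and that 60% respond, and concludes that "we would expect the PRRT group may have approximately 180 patients with complete HRQoL data". Table 5 then gives power of 100%, 98.3% and 84.3% for total declines of 9, 6 and 4.5 points over four time points (0, 6, 12 and 18 months). It assumes SD 18, correlation 0.5 and a Wilks' Lambda F test at 5%.

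Section 5.10.3 counts the 6-, 12- and 18-month surveys from the date each patient completes the baseline survey. It also keeps portal accounts open at least through the end of 2025.

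Table 8 in section 11 sets these due dates:

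- D5, 10/1/2022: "50% of participants (N = 1505) screened, enrolled, and consented to the study"
- E1, 6/1/2023: "75% of participants (N =2258) screened, enrolled, and consented to the study"
- G1, 2/1/2024: "100% of participants (N = 3010) screened, enrolled, and consented to the study"
- G3, 6/30/2024: "Awardee must ensure that all data collection for all study aims as specified in the research plan is completed"
- G4, 6/30/2024: "Awardee must ensure that all analysis and evaluation for all study aims as specified in the Research Plan are completed"

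Public release of the data sets (G6) and primary completion (G9) carry the same 6/30/2024 date, which is also the end of the study period given in section 11.

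**The concern.** The 180 applies the 60% to everyone ever enrolled, as if each patient had 18 months before the data close. A patient enrolled on 2/1/2024 has about 5 months by 6/30/2024 and reaches month 18 in about August 2025. The arithmetic in 9.2.1 makes no allowance for this.

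Table 5 is the only power statement for the Aim 1 primary outcome, which Table 4 marks as powered. If the 6/30/2024 close stands, its n is too large and its power too favourable. If the 180 stands, the close date is wrong, and so are the milestones that depend on it. Both statements are in this protocol, so a separate analysis plan could not settle the matter without changing one of them.

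**Working it through.** **Reproducing the plan.** 3,010 × 0.10 × 0.60 = 180.6, matching the stated 180. For four time points with equal correlation ρ and a linear total change T, the sum of squared deviations of the means is 5T²/9 and the noncentrality is λ = n × (5T²/9) / [SD²(1 − ρ)]. With SD 18 and ρ 0.5 the denominator is 162. At n = 180, λ is 50.0, 22.2 and 12.5 for T = 9, 6 and 4.5. The noncentral F with 3 and 177 degrees of freedom gives 100, 98.4 and 84.8%, within 0.5 points of Table 5. A first-order autoregressive correlation of 0.5 gives 99.4, 81.3 and 54.2% and does not reproduce the table, so equal correlation is used below.

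**Who can finish by the close.** 6/30/2024 minus 18 months is 12/30/2022. Assume that the Table 8 due dates are met, that accrual is linear between them, and that baseline is completed at enrolment.

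- Enrolled by 12/30/2022 (four surveys possible): 1,505 + 753 × 90/243 = 1,784
- Enrolled by 6/30/2023 (at least three): 2,258 + 752 × 29/245 = 2,347
- Enrolled by 12/30/2023 (at least two): 2,258 + 752 × 212/245 = 2,909

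Multiplied by 0.10 × 0.60, these give 107, 141 and 175 of 181 PRRT responders. The responders therefore split into 107, 34, 34 and 6 with four, three, two and one survey.

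**Range.** Any accrual path that meets D5 and E1 on their due dates has between 1,505 and 2,258 enrolled at the cutoff, which gives 90 to 135 complete series. At the 15% PRRT rate that section 9.2 reports for 2019, the central figure is 1,784 × 0.15 × 0.60 = 161.

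**Power.** The complete-series rows use the formula above. The mixed-model rows use generalised least squares with the same covariance, a 3-degree-of-freedom time test and the partial series. At 15% PRRT those series are 161/51/51/9.

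| Case | 9 pts | 6 pts | 5 pts | 4.5 pts |
|---|---|---|---|---|
| Table 5 as stated | 100% | 98.3% | – | 84.3% |
| n = 180, complete series | 100% | 98% | 92% | 85% |
| n = 107, complete series | 99.8% | 86% | 70% | 60% |
| 107/34/34/6, mixed model | 100% | 93% | 80% | 70% |
| n = 161 (15% PRRT), complete series | 100% | 97% | 88% | 80% |
| 161/51/51/9 (15% PRRT), mixed model | 100% | 99% | 94% | 88% |

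For a 10-point change, complete-series power at n = 107 is above 99.9%.

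**The case against.** The strongest reply is that the error may lie in Table 8 and not in the 180. Section 5.10.3 keeps accounts open at least through the end of 2025, and the last enrollee would reach month 18 inside that window. Table 8 also tracks funder milestones, and several of its early due dates have already slipped. This stands in part: the documents do not say which date governs. But account access is not a survey close date, and Table 8 puts data collection, analysis, data release and primary completion all on 6/30/2024. One side has to change.

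A second reply is that the practical loss is small, and this largely stands. Section 7.1 cites 10 points as the widely accepted minimal important difference. The 5-point threshold there comes from a colorectal cancer study, and no NET-specific value is given. Section 9.1.1 plans a mixed model that uses partial series, and 10% PRRT is described as conservative. At 15% with the mixed model, power at 4.5 points is about 88%, above the stated 84.3%. The mixed-model figures may also be low, because they give no credit for surveys from patients outside the 60%.

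It could also be said that the 60% already allows for truncation. Section 9.2.1 calls it a response rate. If it did cover truncation, about 178 PRRT patients (1,784 × 0.10) would be enrolled by the cutoff, and essentially all of them would have to complete four surveys.

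Three stronger readings are tempting but not supported:

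- **The recorded delays already reduce 107.** Table 8 projects the first patient and 25% enrolment late, but if D5 and E1 are still met the count is unchanged. It falls only if one of those slips, and no passage projects that.
- **The 180 in section 9.2.3 fails in the same way.** Section 7.1 takes renal function from laboratory creatinine before and after PRRT cycles, and section 6.1 draws records from two years before diagnosis. The survey cutoff does not limit those series.
- **Aim 1 is underpowered in general.** The 10-point result contradicts that.

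**Conclusion.** The point holds as an inconsistency that makes the stated n and power unsupported by the stated schedule. If 6/30/2024 is the close, 9.2.1 should count about 107 complete PRRT series in place of 180 (90 to 135 if D5 and E1 are met on their dates, 161 at 15% PRRT, fewer if D5 or E1 slips). Among the Table 5 rows, the 4.5-point one is the only one to fall below 80% at n = 107. A 5-point change, which is not a row of Table 5, also does so on complete series and is at about 80% under the mixed model. The count rests on linear accrual between milestones and on a 60% completion rate that does not vary with enrolment date. The documents do not establish that 107 will be the actual number, because they do not settle whether surveys stop in mid-2024 or run into 2025.

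**What to change.** State one survey close date and make section 9.2.1 agree with it.

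(a) If 6/30/2024 stands, give in 9.2.1 the number of PRRT patients who can complete four surveys by then, with the accrual assumption behind it. Restate Table 5 for complete series and for the planned mixed model. The cost is wording, one table and a less favourable stated power.

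(b) If 180 is kept, reconcile the dependent Table 8 milestones with surveys running to about August 2025: G3, G4, G6, G9, the final progress report (G), the draft final report and its revisions (H, J) and the results submission (I, due 1/1/2025). Reconcile the clinical data end dates too: source data to 12/31/2023 in section 4.1, the late-2023 data request in 6.1 and the December 2023 chart review in 6.2. Otherwise the 2024–25 surveys would have no matching treatment data. This costs more, since the milestones must be agreed with the funder and the extraction and chart review would come later.
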